12.7 Product Complaint Reporting

Product complaint reporting and vigilance reporting are applicable, and AEs related to any market-released device during the study must be reported. The reporting of product complaints is not part of the study and should be done in addition to the AE reporting requirements. Refer to local regulations for reporting requirements.

Product Complaint: Any written, electronic, or oral communication that alleges deficiencies related to the identity, quality, durability, reliability, safety, effectiveness, or performance of a medical device that has been placed on the market.

Abuse: Abnormal use (definition acc. #4.1 of Meddev 2.12-1)

Misuse: Use error (definition acc. #4.20 of Meddev 2.12-1). It is the responsibility of the Investigator to report all product complaint(s) associated with a medical device distributed by Medtronic, regardless of whether they are related to intended use, misuse, or abuse of the product. Reporting must be done immediately and via the regular channels for market-released products. The reporting of product

complaints by the clinical team must be done according to the local Standard Operating Procedures. Medtronic will notify the RAs (e.g., CA) as applicable for the following incidents immediately upon learning of them and is not limited to AEs and DDs only:

Any malfunction or deterioration in the characteristics and/or performance of a device, as well as any inadequacy in the labeling or instructions for use which led or might have led to the death or serious deterioration in the state of health of a subject, user, or other person.

Any technical or medical reason resulting in withdrawal of a device from the market by the manufacturer.

Any serious deterioration in the state of health, including:

Life-threatening illness or injury

Permanent impairment of a body function or permanent damage to a body structure

A condition necessitating medical or surgical intervention to prevent permanent impairment of a body function or permanent damage to a body structure.

13. Data Review Committees

13.1 Clinical Events Committee Review

An external, independent CEC will be utilized to adjudicate AEs during the study. The CEC will consist of a minimum of three (3) non-Medtronic employed physicians that are not participating Investigators for the study, including a CEC chairperson. Medtronic personnel may attend a CEC meeting but will be non-voting members.

The CEC will be external to Medtronic and independent of the study Investigators. The members will have specialties appropriate to the therapeutic areas and meet requirements established in the CEC Charter. The CEC Charter will define the CEC processes for member selection, meeting frequency, roles and responsibilities, procedures and record keeping. Prior to making a final adjudication decision, the CEC may request clarification and/or additional information from the Principal Investigator who reported the event.

The site investigator may agree or disagree with the CEC's adjudication, and the eCRF documenting the AE may be updated accordingly. Ultimately, the CEC's adjudication will be captured in the eCRF used for data analysis.

13.2 CRO/Core Lab(s)

This information may be subject to change during the course of the study. Periodic updates to study contact information will be sent to study sites as needed.

Table 11. CRO and Core Laboratory Information

Contact Information	Role
[REDACTED]	Review of electronic case report forms and management of discrepancies
[REDACTED]	Independent clinical events adjudication committee

14. Statistical Design and Methods

This section presents statistical considerations for the study design and provides a high-level description of planned analyses and reporting. If necessary, real-world evidence (RWE) may be supplemented to the data collected in this prospective trial and included in the study analyses. More technical details will be provided in a separate statistical analysis plan (SAP) that will be finalized and approved prior to database lock. Any deviations to the pre-specified statistical analyses will be noted in the final clinical study report.

14.1 General Aspects of Analysis

Data analysis will be performed by Medtronic or its designee.

Descriptive statistics will be used to summarize study outcomes. Continuous variables will be summarized using number of subjects (n), mean, standard deviation, median, IQR and ranges. Categorical variables will be summarized using frequencies and percentages.

Subject disposition will be illustrated in a CONSORT diagram. Subject visits will be tabulated and compliance to visit schedules and visit windows will be summarized.

All statistical analyses will be performed using Statistical Analysis System (SAS) for Windows (version 9.4 or higher, SAS Institute Inc. Cary, NC) or other widely accepted statistical or graphical software.

All tests of treatment effects will be conducted at a two-sided alpha level of 0.05 unless otherwise stated. A P-value less than 0.05 is considered statistically significant. Confidence intervals will be presented at the 95% level unless otherwise stated.

The study will be considered successful when the primary effectiveness and safety endpoints are met.

14.2 Analysis Execution

The study safety and performance analyses will occur after all subjects complete the 30-day follow-up. The analyses will include both primary and secondary 30-day objectives. A clinical study report will be prepared once all data collection has ended and all subjects have completed the 30-day follow-up or have been exited. Annual progress reports will be prepared for oncologic subjects through 5 years. A final report will be completed at the end of the 5-year follow-up that will include the 5-year secondary analyses.

All available data will be included in the analysis. Sensitivity analysis may be performed for missing data to assess the robustness of study results as described in **Section 14.11**.

14.3 Interim Analysis

No interim analysis is planned for this study. Outcomes through 30 days for the first 15 roll-in cases will be summarized descriptively and provided to the FDA for initial review without statistical inferences. The roll-in subjects will be included in the final data analysis for the study.

14.4 Primary Objectives

A systematic literature search was conducted for Jan 1, 2018 – Jun 13, 2023 to identify published clinical data on the use of RAS devices in nephrectomy, prostatectomy, and cystectomy procedures. Literature data reporting on the study objectives were used to determine the appropriate sample sizes and performance goals for each endpoint and surgery cohort. The full bibliography of all 130 publications supporting the updated performance goals is included in **Section 17.1**.

14.4.1 Primary Objective #1 (Effectiveness)

The primary effectiveness objective of this study is to confirm that the Medtronic Hugo™ RAS System is effective when used for urologic robotic assisted surgery. The primary effectiveness endpoint is the surgical success rate, as defined in **Section 6.4.2**.

The primary effectiveness hypothesis is to test if the surgical success rate is above the performance goal. Based on published data and clinical practice, a surgical success rate of 90% or higher is expected. A performance goal of 85% (based on the literature) is pre-defined to evaluate the surgical success rate. Let P be the surgical success rate in this study. The statistical hypothesis is formulated as follows:

$$H_0: P \leq 85\% \text{ vs. } H_a: P > 85\%$$

The hypothesis will be tested using the Clopper-Pearson exact method at one-sided alpha of 0.025.

Performance Goal Rationale and Sample Size

Analyses were performed based on available literature. Point estimates along with 95% and 99% predicted intervals were calculated to provide plausible range of potential effect size. Clinically meaningful margins and statistical precisions have been taken into account to determine the appropriate performance goals. The calculation details and rationales are summarized in the following table.

Surgery Type	PG	Sample Size	Rationale
Nephrectomy	85%	141	The mean effect size for conversions is 0.022 with a 95% confidence interval of 0.017 to 0.029. The 95% prediction interval is 0.005 to 0.098. The 99% prediction interval is 0.003 to 0.153. A performance goal of 85% for surgical success rate was set, which is equivalent to 0.15 as the conversion rate (1-success rate), aligned with the 95% to 99% of predictive intervals upper limit of 0.098 to 0.153. A single-group design will be used to test whether the proportion is greater than 0.85 ($H_0: P \leq 0.85$ versus $H_a: P > 0.85$). The comparison will be made using a one-sided, one-sample exact test, with a target Type I error rate (α) of 0.025. To detect a difference ($P_1 - P_0$) of 0.102 with a sample size of 126, which accounts for 10% attrition from the overall study sample size of up to 141, the power is 0.96.
Prostatectomy			
Cystectomy			

14.4.2 Primary Objective #2 (Safety)

The primary safety objective of this study is to confirm that the Medtronic Hugo™ RAS System is safe when used for urologic robotic assisted surgery. The primary safety endpoint is the rate of subjects with major complications (meeting Grade III criteria or higher per the Clavien-Dindo Classification system) from the first incision through 30 days post-procedure. Further details can be found in **Section 6.4.2**.

The primary safety hypothesis is to test the overall 30-day major complication rate (i.e., rate of subjects with one or more major complications) against a performance goal. Since the safety profiles or major complication rates are very different among the three surgeries, a separate performance goal is pre-specified for each of the three surgery types (as per FDA recommendation). The performance goals are determined based on published literature data.

Let R be the 30-day major complication rate, and PG be performance goal for a specific surgery group. The statistical hypothesis is formulated as follows:

$$H_0: R \geq PG \text{ vs. } H_a: R < PG$$

The hypothesis will be tested using the Clopper-Pearson exact method and the null hypothesis will be rejected if one-sided p-value is significant comparing to alpha determined after multiplicity adjustment as described in **Section 14.12**.

Performance Goal Rationale and Sample Size

The literature search was performed based on available literature for each of the three surgery types (nephrectomy, prostatectomy, cystectomy). Point estimates along with 95% and 99% predicted intervals were calculated to provide plausible range of potential effect sizes. Clinically meaningful margins and statistical precisions have been taken into account to determine the appropriate performance goals. In some situations, considerations were also given to align with the studies from comparable sample sizes. The calculation details and rationales are summarized in the following table.

All sample size calculations are based on exact test. Presuming a one-sample proportion and one-sided test with the least alpha of 0.008 (0.025/3) when performing three hypothesis testing (nephrectomy, prostatectomy, and cystectomy, respectively) and adjusting for multiplicity in primary safety objectives, sample size justification and performance goals are described as below:

Surgery Type	Performance Goal (PG)	Sample Size	Rationale
Nephrectomy	20%	55	The mean effect size is 0.029 with a 95% confidence interval of 0.022 to 0.038. The 95% prediction interval is 0.017 to 0.047. The 99% prediction interval is 0.014 to 0.058. A performance goal of 0.20, while greater than the predicted interval, broadly aligns with the upper limits for each nephrectomy study with a comparable study size (95% upper limits ranging from 0.100 to 0.539) and is clinically appropriate. A performance goal of 0.20, assuming a sample size of up to 55 (with 10% attrition n=49), one-sided alpha of 0.008 (Bonferroni Correction), and mean effect size of 0.029, results in a power of 95%.
Prostatectomy	20%	55	The mean effect size is 0.029 with a 95% confidence interval of 0.016 to 0.051. The 95% prediction interval is 0.004 to 0.173. The 99% prediction interval is 0.002 to 0.316. A performance goal of 0.20 (20%), is clinically appropriate. A performance goal of 0.20, assuming a sample size of up to 55 (with 10% attrition n=49), one-sided alpha of 0.008 (Bonferroni Correction), and mean effect size of 0.029, results in a power of 95%.
Cystectomy	45%	31	The mean effect size is 0.162 with a 95% confidence interval of 0.132 to 0.198. The 95% prediction interval is 0.047 to 0.354. The 99% prediction interval is 0.024 to 0.520. A performance goal of 0.45 (45%), is clinically appropriate. A mean effect size of 14.1% is used in the sample size calculations as it is more aligned with internal assumptions of the performance of Hugo. A performance goal of 0.45, assuming a sample size of up to 31 (with 10% attrition n=27), one-sided alpha of 0.008 (Bonferroni Correction), and mean effect size of 0.141, results in a power of 83%.

14.5 Secondary Objectives

The secondary objective of this study is to demonstrate the Medtronic Hugo™ RAS System performs as intended when used in urologic robotic assisted surgery. The secondary endpoints of this study will assess the overall performance of the Medtronic Hugo™ RAS System when used for urologic robotic surgery.

The following short-term secondary endpoints will be assessed:

Medtronic Business Restricted

This document is electronically controlled

CONFIDENTIAL 056-F275 Rev E Clinical Investigation Plan Template

- Complication rate: Overall rate of subjects with one or more major complications (Clavien-Dindo Grade I or higher), from the first incision through 30 days post-procedure
- Operative time
- Intraoperative estimated blood loss (mL)
- Transfusion rate
- Rate of device-related conversion
- Hospital length of stay
- Readmission rate (through 30 days)
- Reoperation rate (through 30 days)
- Mortality rate (through 30 days)
- Rate of device deficiencies

The following long-term secondary endpoints will be assessed through 5 years in oncologic subjects:

- Overall survival
- Progression-free survival
- Disease-free survival

Descriptive statistics will be used to summarize secondary endpoints. In addition, performance goals are pre-specified based on meta-analysis of published study data as well as considerations of clinically meaningful margins and statistical confidences for most secondary endpoints (see details below; the full bibliography of 130 publications supporting the updated performance goals is included in **Section 17.1**). 95% confidence intervals might be provided as appropriate. Statistical evaluations for secondary objectives with performance goals are not powered in this study. Additionally, the secondary endpoints are planned to be analyzed using descriptive statistics, which broadly negate the need for multiplicity adjustments.

The role of the secondary endpoints is to explore additional effects and outcomes associated with either the procedure or the disease state. The pre-specified performance goals serve as benchmarks for interpretation rather than thresholds for statistical significance of clinical trial success in this study.

Performance Goals for Secondary Endpoints

Performance goals are specified for each of the secondary endpoints. The details are summarized in the following table.

Medtronic Expand URO Clinical Investigation Plan

MDT19051EINURO

Version 9.0

Page 73 of 111

Medtronic

Endpoint	Procedure Type	PG	Rationale
Rate of subjects with complications (through 30 days)	Nephrectomy	30.0%	The mean effect size is 0.116 with a 95% confidence interval of 0.087 to 0.152. The 95% prediction interval is 0.048 to 0.252. A performance goal of 0.30 is clinically appropriate for descriptive comparison.
	Prostatectomy	45.0%	The mean effect size is 0.056 with a 95% confidence interval of 0.038 to 0.082. The 95% prediction interval is 0.006 to 0.372. A performance goal of 0.45 is clinically appropriate for descriptive comparison.
	Cystectomy	85.0%	The mean effect size is 0.417 with a 95% confidence interval of 0.272 to 0.577. The 95% prediction interval is 0.080 to 0.854. A performance goal of 0.85 is clinically appropriate for descriptive comparison.
Operative time (min)	Nephrectomy	255 min	The mean effect size is 170.1 with a 95% confidence interval of 155.5 to 184.7. The 95% prediction interval is 81.9 to 304.9. A performance goal of 255 minutes is clinically appropriate for a descriptive comparison.
	Prostatectomy	340 min	The mean effect size is 190.6 with a 95% confidence interval of 169.7 to 211.5. The 95% prediction interval is 96.9 to 324.8. A performance goal of 340 minutes is clinically appropriate for a descriptive comparison.
	Cystectomy	500 min	The mean effect size is 376.2 with a 95% confidence interval of 315.9 to 436.6. The 95% prediction interval is 185.6 to 682.1. A performance goal of 500 minutes is clinically appropriate for a descriptive comparison.
Intraoperative estimated blood loss (mL)	Nephrectomy	490 mL	The mean effect size is 181.0 with a 95% confidence interval of 131.5 to 230.5. The 95% prediction interval is 34.3 to 507.7. A performance goal of 490 mL is clinically appropriate for a descriptive comparison.
	Prostatectomy	500 mL	The mean effect size is 193.3 with a 95% confidence interval of 168.2 to 218.4. The 95% prediction interval is 54.7 to 486.5. A performance goal of 500 mL is clinically appropriate for a descriptive comparison.

Medtronic Business Restricted

This document is electronically controlled

CONFIDENTIAL 056-F275 Rev E Clinical Investigation Plan Template

Medtronic Expand URO Clinical Investigation Plan

MDT19051EINURO

Version 9.0

Page 74 of 111

Medtronic

Endpoint	Procedure Type	PG	Rationale
	Cystectomy	500 mL	The mean effect size is 133.0 with a 95% confidence interval of 102.6 to 163.4. The 95% prediction interval was not able to be obtained due to a lack of data. As there are few literature cohorts available for this endpoint, the performance goals of the other two surgical cohorts were considered in setting this endpoint's performance goal of 500.
Transfusion rate	Nephrectomy	30%	The mean effect size is 0.079 with a 95% confidence interval of 0.056 to 0.11. The 95% prediction interval is 0.021 to 0.257. A performance goal of 0.30 is clinically appropriate for descriptive comparison.
	Prostatectomy	60%	The mean effect size is 0.020 with a 95% confidence interval of 0.011 to 0.037. The 95% prediction interval is 0 to 0.534. A performance goal of 0.60 is clinically appropriate for descriptive comparison.
	Cystectomy	55%	The mean effect size is 0.133 with a 95% confidence interval of 0.050 to 0.308. The 95% prediction interval is 0.004 to 0.869. While below the 95% prediction interval upper limit, a performance goal of 0.550 is better aligned for a descriptive comparison.
Rate of device-related conversion	Nephrectomy	15%	The literature search failed to identify studies that reported on device-related conversions. Device related conversions are expected to be a fraction of the total conversions. Conversion Rate = 100% - Surgical Success Rate, which has a performance goal of 85%. Thus, a 15% performance goal is assumed for conversions.
	Prostatectomy	15%	The literature search failed to identify studies that reported on device-related conversions. Device related conversions are expected to be a fraction of the total conversions. Conversion Rate = 100% - Surgical Success Rate, which has a performance goal of 85%. Thus, a 15% performance goal is assumed for conversions.
	Cystectomy	15%	The literature search failed to identify studies that reported on device-related conversions. Device related conversions are expected to be a fraction of the total conversions. Conversion Rate = 100% - Surgical Success Rate, which has a performance goal of 85%. Thus, a 15% performance goal is assumed for conversions.

Medtronic Business Restricted

This document is electronically controlled

CONFIDENTIAL 056-F275 Rev E Clinical Investigation Plan Template

Medtronic Expand URO Clinical Investigation Plan

MDT19051EINURO

Version 9.0

Page 75 of 111

Medtronic

Endpoint	Procedure Type	PG	Rationale
Hospital length of stay [LOS] (days)	Nephrectomy	7 days	The mean effect size is 3.7 with a 95% confidence interval of 3.1 to 4.2. The 95% prediction interval is 1.1 to 8.5. A performance goal of 7 days is clinically appropriate for a descriptive comparison.
	Prostatectomy	11 days	The mean effect size is 4.9 with a 95% confidence interval of 4.0 to 5.8. The 95% prediction interval is 0.6 to 15.0. A performance goal of 11 days is clinically appropriate for a descriptive comparison.
	Cystectomy	7 days	The mean effect size is 5.6 with a 95% confidence interval of 4.9 to 6.2. The 95% prediction interval was not able to be obtained due to lack of data. The longest literature-reported hospital length of stay was 5.9 days, applying a 20% relative margin to this gives 7.08 days. Thus, a performance goal of 7 days was set and deemed to be clinically appropriate.
Readmission rate (through 30 days)	Nephrectomy	16.8%	The mean effect size was 0.063 with a 95% confidence interval of 0.028 to 0.132. The 95% prediction interval was not able to be obtained due to a lack of data. The highest literature-reported readmission rate within 30 days was 0.068, applying a 10% absolute margin to this gives 0.168. Thus, a performance goal of 16.8% was set and deemed to be clinically appropriate.
	Prostatectomy	30.0%	The mean effect size is 0.050 with a 95% confidence interval of 0.025 to 0.097. The 95% prediction interval is 0.010 to 0.224. Thus, a performance goal of 30.0% was clinically appropriate for descriptive comparison.
	Cystectomy	39.4%	The mean effect size was 0.136 with a 95% confidence interval of 0.033 to 0.419. The 95% prediction interval was not able to be obtained due to a lack of data. The highest literature-reported readmission rate within 30 days was 0.229, applying a 10% absolute margin to this gives 0.329. Thus, a performance goal of 39.4% was set and deemed to be clinically appropriate.
Reoperation rate (through	Nephrectomy	25.6%	There was no literature found, therefore the prostatectomy performance goal was leveraged to assign a performance goal of 25.6%.

Medtronic Business Restricted

This document is electronically controlled

CONFIDENTIAL 056-F275 Rev E Clinical Investigation Plan Template

Medtronic Expand URO Clinical Investigation Plan

MDT19051EINURO

Version 9.0

Page 76 of 111

Medtronic

Endpoint	Procedure Type	PG	Rationale
30 days)	Prostatectomy	25.6%	The mean effect size was 0.062 with a 95% confidence interval of 0.005 to 0.469. The 95% prediction interval was not able to be obtained due to a lack of data, as there were only two cohorts as part of this meta-analysis. The highest literature-reported reoperation rate within 30 days was 0.156, applying a 10% absolute margin to this gives 0.256. Thus, a performance goal of 25.6% was set and deemed to be clinically appropriate.
	Cystectomy	25.6%	There was no literature found, therefore the prostatectomy performance goal was leveraged to assign a performance goal of 25.6%.
Mortality rate (through 30 days)	Nephrectomy	24.3%	Limited to two cohorts from one study, the performance goal is derived based on the individual cohort upper limits of 0.143. A value of 0.243 provides 10% margin on the upper limit, while remaining clinically appropriate.
	Prostatectomy	21%	Limited to one cohort, the performance goal is derived based on the individual cohort upper limit of 0.110. A value of 0.210 provides 10% margin on the upper limit, while remaining clinically appropriate.
	Cystectomy	35.1%	This analysis was based on 6 cohorts. As there was no variance between cohorts, the performance goal is derived based on the individual cohort upper limits of 0.040 to 0.251. A value of 0.351 provides 10% margin on the upper limit, while remaining clinically appropriate.
Rate of device deficiencies	Nephrectomy	20%	Device specific deficiencies were not reported in the literature. Recognizing that device deficiencies include those of preference and not all will impact the safety or performance of the device, a clinically appropriate performance goal of 20% has been selected.
	Prostatectomy	20%	Device specific deficiencies were not reported in the literature. Recognizing that device deficiencies include those of preference and not all will impact the safety or performance of the device, a clinically appropriate performance goal of 20% has been selected.

Medtronic Business Restricted

This document is electronically controlled

CONFIDENTIAL 056-F275 Rev E Clinical Investigation Plan Template

Medtronic Expand URO Clinical Investigation Plan

MDT19051EINURO

Version 9.0

Page 77 of 111

Medtronic

Endpoint	Procedure Type	PG	Rationale
	Cystectomy	20%	Device specific deficiencies were not reported in the literature. Recognizing that device deficiencies include those of preference and not all will impact the safety or performance of the device, a clinically appropriate performance goal of 20% has been selected.
Overall survival (OS) (5 years)	Nephrectomy	51.6%	The mean effect size is 0.931 with a 95% confidence interval of 0.614 to 0.991. The 95% prediction interval was 0.0 to 1.00. Thus, a performance goal of 0.516 was clinically appropriate.
	Prostatectomy	50%	The mean effect size is 0.954 with a 95% confidence interval of 0.887 to 0.982. The 95% prediction interval is 0.0 to 1.0. A performance goal of 0.50 is clinically appropriate for descriptive comparison.
	Cystectomy	35%	The mean effect size is 0.645 with a 95% confidence interval of 0.571 to 0.714. The 95% prediction interval is 0.426 to 0.817. A performance goal of 0.35 is clinically appropriate for descriptive comparison.
Progression-free survival (PFS) (5 years)	Nephrectomy	15%	Progression-free survival at 5-years is not reported within the literature. Therefore, the performance goals will be based on a function of those for overall survival, roughly 1/3, and are clinically meaningful.
	Prostatectomy	15%	Progression-free survival at 5-years is not reported within the literature. Therefore, the performance goals will be based on a function of those for overall survival, roughly 1/3, and are clinically meaningful.
	Cystectomy	10%	Progression-free survival at 5-years is not reported within the literature. Therefore, the performance goals will be based on a function of those for overall survival, roughly 1/3, and are clinically meaningful.
Disease-free survival (DFS) (5 years)	Nephrectomy	15%	Disease-free survival at 5-years is not reported within the literature. Therefore, the performance goals for progression-free survival will be leveraged and are clinically meaningful.
	Prostatectomy	15%	Disease-free survival at 5-years is not reported within the literature. Therefore, the performance goal for progression-free survival will be leveraged and are clinically meaningful.

Medtronic Business Restricted

This document is electronically controlled

CONFIDENTIAL 056-F275 Rev E Clinical Investigation Plan Template

Medtronic Expand URO Clinical Investigation Plan

MDT19051EINURO

Version 9.0

Page 78 of 111

Medtronic

Endpoint	Procedure Type	PG	Rationale
	Cystectomy	10%	Disease-free survival at 5-years is not reported within the literature. Therefore, the performance goal for progression-free survival will be leveraged and are clinically meaningful.

Medtronic Business Restricted

This document is electronically controlled

CONFIDENTIAL 056-F275 Rev E Clinical Investigation Plan Template

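### The cystectomy 30-day readmission goal (39.4%) does not follow from its own stated derivation, which gives 32.9%

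*Protocol*

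**What the plan says.** Protocol Section 14.5 sets a performance goal for each secondary endpoint by surgery type. For 30-day readmission after cystectomy no prediction interval could be obtained, so the goal is built from the literature maximum: "The highest literature-reported readmission rate within 30 days was 0.229". The row then reads: "applying a 10% absolute margin to this gives 0.329. Thus, a performance goal of 39.4% was set and deemed to be clinically appropriate". The PG column for the row also shows 39.4%. The pooled mean given in the same row is 0.136, with a 95% confidence interval of 0.033 to 0.419.

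Two other rows use the same construction and nearly the same words. Nephrectomy readmission, from a maximum of 0.068: "applying a 10% absolute margin to this gives 0.168. Thus, a performance goal of 16.8% was set and deemed to be clinically appropriate". Prostatectomy reoperation, from a maximum of 0.156: "applying a 10% absolute margin to this gives 0.256. Thus, a performance goal of 25.6% was set and deemed to be clinically appropriate".

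Section 14.5 also says that the secondary goals are benchmarks for interpretation, not thresholds for trial success. SAP 7.9.3.2 plans no hypothesis test for them. SAP 7.9.3.5 reports readmission by surgery type as a count and proportion with a 95% confidence interval. SAP 10.1 gives no values of its own and refers back to Protocol Section 14.5 for both goals and justifications.

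**The concern.** The row computes one number and states a different one as its consequence. The addition of 0.10 to 0.229 is correct; the break comes between 0.329 and 39.4%. No second margin, rounding step or clinical override is given to bridge them. The closing remark that the goal is clinically appropriate cannot serve as one, because the same remark closes the nephrectomy readmission and prostatectomy reoperation rows, where the goal equals base plus 10 points exactly.

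The stake is interpretive. A descriptive benchmark is only as good as its stated basis, and here the basis contradicts the figure in the lenient direction. Because the SAP imports the table by reference, it offers no second source to settle the matter, and the clinical study report would have to cite a goal that its own justification does not support.

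**Working it through.** **Inputs** (all Protocol Section 14.5 unless noted): base 0.229; margin 10 points absolute; stated intermediate result 0.329; stated goal 39.4%. Cystectomy cohort of up to 31, or 27 after 10% attrition (Protocol 14.4.2).

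**Step 1: reproduce the row.** Goal = base + margin = 0.229 + 0.10 = 0.329, or 32.9%. The plan's intermediate figure is reproduced; its goal is not. Difference: 0.394 − 0.329 = 0.065, or 6.5 percentage points.

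**Step 2: apply the same check to every row that states both a base and a margin.**

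| Row | Derivation | Result | Goal |
|---|---|---|---|
| Readmission, nephrectomy | 0.068 + 0.10 | 0.168 | 16.8% |
| Reoperation, prostatectomy | 0.156 + 0.10 | 0.256 | 25.6% |
| Mortality, nephrectomy | 0.143 + 0.10 | 0.243 | 24.3% |
| Mortality, prostatectomy | 0.110 + 0.10 | 0.210 | 21% |
| Mortality, cystectomy | 0.251 + 0.10 | 0.351 | 35.1% |
| Length of stay, cystectomy | 5.9 × 1.20 | 7.08 days | 7 days |
| **Readmission, cystectomy** | **0.229 + 0.10** | **0.329** | **39.4%** |

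Six of seven reconcile; length of stay does so after rounding. The three mortality rows do not say whether their 10% is absolute or relative (for example "A value of 0.351 provides 10% margin on the upper limit, while remaining clinically appropriate"). The absolute reading is the one that fits. A relative margin would give 0.143 × 1.1 = 0.157, 0.110 × 1.1 = 0.121 and 0.251 × 1.1 = 0.276, none of which is the stated value.

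**Step 3: look for a route to 39.4%.**
- 20% relative on the base, the table's other margin rule: 0.229 × 1.2 = 0.275.
- 15 or 20 points absolute: 0.379 or 0.429.
- 10% relative on top of 0.329: 0.362.
- 20% relative on top of 0.329: 0.3948, which rounds to 39.5%; no such second step is described.
- Pooled mean plus 10 points: 0.136 + 0.10 = 0.236. Upper confidence limit: 0.419.

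None gives 39.4%. If only one input is wrong, the base would have to be 0.394 − 0.10 = 0.294, or the margin 0.394 − 0.229 = 16.5 points. Neither is stated, and both inputs could be wrong together.

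**Step 4: effect on the reading.** The plan does not say how a result is to be compared with the goal, so two conventions are shown.

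*Observed rate at or below the goal.* The largest count that meets it is the whole-number part of goal × n:
- n = 31: 0.394 × 31 = 12.2, so 12; 0.329 × 31 = 10.2, so 10.
- n = 27: 0.394 × 27 = 10.6, so 10; 0.329 × 27 = 8.9, so 8.

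The gap is two subjects at every n from 27 to 31. The results whose reading changes are 11 or 12 of 31 (35.5%, 38.7%) and 9 or 10 of 27 (33.3%, 37.0%).

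*Upper limit of the exact two-sided 95% interval below the goal.* The largest counts are 6 against 4 at n = 31 and 5 against 3 at n = 27. The gap is one subject at n = 28 and n = 29.

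Binomial probability that the result falls where the two goals give different readings, at assumed true rates:

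| True rate (assumed) | Observed rate, n = 31 | Observed rate, n = 27 | Upper limit, n = 31 | Upper limit, n = 27 |
|---|---|---|---|---|
| 0.136 (pooled mean) | 0.2% | 0.7% | 30% | 36% |
| 0.229 (highest reported) | 6% | 12% | 28% | 29% |
| 0.329 | 26% | 30% | 6% | 7% |

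**The case against.** The strongest reply is that little depends on this row. The endpoint is secondary and descriptive, no test is planned, and no trial conclusion turns on it. That is correct and limits the weight of the point, but it does not make the row right.

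A second reply is that Section 14.5 allows goals to reflect clinical margins as well as literature figures, and that other rows reach a goal without arithmetic: prostatectomy readmission is set at 30.0% against an upper prediction limit of 0.224. So the connecting word before 39.4% proves little by itself. That too is fair. The cystectomy row differs because it states its margin and its computed result, and then departs from that result without comment. Where the table knowingly departs from its anchor it says so, as it does for cystectomy transfusion.

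A third reply is that the size of the effect depends on a comparison rule the plan does not give. This stands. Under the observed-rate rule a changed reading is unlikely if readmission is near the literature mean; under the interval rule it is not unlikely there. The objection shows that the effect depends on the convention, not that it is always negligible.

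**Conclusion.** The concern holds. The cystectomy readmission goal of 39.4% contradicts its own derivation by 6.5 percentage points, and it is the only one of the seven margin-derived rows that fails to reconcile. The count of seven takes the mortality margins as absolute. In subjects, the discrepancy is two readmissions when the observed rate is compared with the goal, and one or two when the interval's upper limit is compared, for cohorts of 27 to 31. The probabilities of a changed reading rest on assumed true rates.

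The inconsistency is certain; which figure is wrong is not. The value 32.9% is what the stated inputs yield, and is not shown to be the intended goal. Primary endpoints, multiplicity control, power and sample size are untouched.

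**What to change.** Check the row against the sponsor's literature file. If 0.229 and the 10-point margin are right, set the goal to 32.9% in both the PG column and the rationale. If 39.4% was intended, correct the base rate or margin, or add the missing reason, so that the text leads to it. It would help to state in the same edit whether results are compared with the secondary goals by point estimate or by confidence limit.

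The cost is one table row. Protocol Section 16.6 requires FDA and IRB approval before a revision is implemented at a site, so the correction can travel with the next revision; the SAP follows by reference. No subjects are added. SAP Section 3 shows that a summary of the first 15 patients already exists, so the change record should state that the correction came from the literature file alone and not from study data. If 32.9% proves right, the only downside for the sponsor is a stricter descriptive benchmark.
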